12.2. Screening Data

Demographics will be tabulated by participant and summarized by cohort and treatment group. Eligibility assessments at baseline, including medical/surgical history data and physical examination data (including height and weight), will be listed for each participant.

12.3. Safety/Tolerability Data

In general, safety analyses will be performed based on Safety Analysis Set, which include all enrolled subjects who receive at least one dose of study drug (placebo or active). Results will be summarized by population (NHV and CF) and cohort. Placebo subjects from each cohort will be pooled by population.

Treatment-emergent AEs will be summarized by System Organ Class (SOC) and Preferred Term (PT), classified from verbatim terms, with MedDRA version 23.0 or later. The incidence and percentage of participants with at least 1 occurrence of a PT will be included, per the most severe grade using a 3-point scale (mild, moderate, severe). The number of events per Preferred Term will also be summarized. Causality (relationship to study treatment) will be summarized separately.

The incidence and frequency of treatment-emergent AEs, SAEs, related AEs, related SAEs and AEs leading to withdrawal, dose modification, or treatment discontinuation will be summarized by population and cohort by SOC and Preferred Terms. All AEs, SAEs will also be summarized in listings. The duration of AEs will be determined and included in listings, along with the action taken and outcome.

Laboratory parameters will be summarized at each scheduled time point using descriptive statistics. The incidence of laboratory abnormalities will be summarized. Results for variables that are not coded will be presented in the listings as “below, within, and above” the normal limits of the laboratory. Pregnancy test results will be listed.

Vital sign measurements will be summarized at each scheduled time point using descriptive statistics. Physical examination findings will be summarized by time point and presented in patient listings.

ECG parameters at each scheduled study visit, changes from baseline and qualitative assessments will be summarized.

12.4. Immunogenicity (Anti-drug Antibodies) Data

Changes from assay negative to positive will be summarized by dose and time to positive. Descriptive statistics of immunogenicity parameters will include mean, SD, minimum, and maximum.

12.5. Pharmacokinetic Data

Plasma concentrations of ARO-ENaC collected at specified time points post-dose from all participants at different dose levels will be used to calculate the following single dose pharmacokinetic parameters (Table 6):

Table 6: Definitions of Pharmacokinetic Parameters to be Assessed

AUC ₀₋₂₄	The area under the plasma concentration versus time curve from 0 to 24 hours
AUC _{inf}	The area under the plasma concentration versus time curve from zero to infinity
C _{max}	The maximum plasma concentration will be obtained directly from the plasma concentration time profile
t _{max}	The time to maximum plasma concentration will be obtained by inspection
t _{1/2}	The half-life will be calculated by the equation $t_{1/2} = \ln(2)/k_{el}$

Additional PK parameters may be calculated as needed. The pharmacokinetic parameters will be determined using non-compartmental method(s). Descriptive statistics of pharmacokinetic parameters will include mean, standard deviation (SD), and coefficient of variation (CV), minimum and maximum. Dose-related trends in pharmacokinetic parameters will be assessed.

Pharmacokinetic parameters will be tabulated and summarized by dose level. The concentration-time profiles for each participant and the mean concentration-time profiles by dose level will be plotted with concentration presented on both linear and logarithmic scales.

Statistical analysis will be performed on the pharmacokinetic parameters using validated statistical software.

12.6. Pharmacodynamic/Efficacy Data

Descriptive statistics will be performed by scheduled study visit on the following measures of efficacy and pharmacodynamic activity:

- *Spirometry (ppFEV1)*
- *Revised Cystic Fibrosis Questionnaire (respiratory domain)*
- *Lung Clearance Index*
- *Rate of CF Exacerbations*
- *BMI*
- *ENaC mRNA expression from bronchoscopic samples*

Efficacy data for CF patients will be analyzed by cohort. Placebo subjects from each cohort will be pooled. Efficacy analyses will be completed based on Safety Analysis Set, which include all enrolled subjects who receive at least one dose of study drug (placebo or active). CF patients will be analyzed in aggregate and also separately based on CFTR mutation status and based on use or no use of a stable regimen (last 2 months) of CFTR modulators/correctors as well as use or no use of inhaled hypertonic saline.

12.7. Data Recording and Quality Control

Source documents must be maintained for each participant in the study, consisting of all demographic and medical information, including clinical laboratory data, and entered into the EDC system within five days of the subject visit. A copy of the signed informed consent form must be retained. All information on the eCRFs must be traceable to these source documents in the participant's file.

Data recorded in all participants' eCRFs will be subjected to a quality control review.

12.8. Handling Missing and Incomplete Data

Partial or missing dates of adverse events and concomitant medications will be imputed. Adverse events with missing severity and/or possible relationship to treatment will be included in the all adverse events analyses, except by severity grade and treatment-related. Every effort will be made to obtain complete dates for deaths. Details of the imputation algorithms will be specified in the statistical analysis plan.

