6.1. Primary Endpoint

1. The incidence and frequency of adverse events over time through end of study using escalating multiple doses in NHVs and in CF patients.

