### 8.2 Handling of Missing and Incomplete Data

Missing values will not be imputed, except in the case of determining treatment-emergent status for AEs, concomitant status for medication and procedures, and for missing or partial dates where a complete date is required for calculations.

Missing	Imputation	Exception
Day	01	Default to Study Day 1 if an AE, medication/procedure starts the same year and month as Study Day 1 and the end date has same year and month as Study Day 1 or later.
Day / Month	01 / Jan	Default to Study Day 1 if an AE, medication/procedure starts the same year as Study Day 1 and the end date has same year as Study Day 1 or later.
Day / Month / Year	To calculate a missing start date: 

If a partial or complete stop date is present:

Stop date < first dosing date: impute January 1 of the stop year

Stop date <math>\geq</math> first dosing date: impute the date of first dose

If it is unknown whether the stop date is < or <math>\geq</math> first dosing date due to a missing or partial stop date, or if a stop date is not

	

	collected: impute date of first dose.	
--	---------------------------------------	--

Medications and procedures with missing or partial end dates will be assumed to be concomitant unless a partial end date documents it as ending prior to treatment.

The original missing or partial date, the imputed complete date, and an indicator variable that indicates which dates were imputed will be retained in the database. Dates will be presented as collected in all listings. Imputed dates will not be presented in listings but may be used for summary tables.

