#### **9.5.1 Adverse Events**

AEs will be recorded from time of signed consent through to EOS. The PI and clinical facility staff are responsible for detection, recording and reporting of events that meet the criteria and definition of AEs. The investigator will determine the severity and relationship of an AE associated with use of the study drug, and will identify serious adverse events (SAEs). All AE data summaries will report these as recorded on the eCRF.

MedDRA version 23.0 or later will be used to code all events categorized as AEs to a SOC and PT.

An overall summary of AEs will be provided. The overall summary will include the number and percent of subjects experiencing an event as well as the number of events in each of the following

---

categories: AEs, TEAEs, treatment-related TEAEs, SAEs, TESAEs, treatment-related TESAEs, and AEs resulting in study drug withdrawal, study discontinuation, and death. Categories are not mutually exclusive.

Descriptive statistics summaries of subject incidence of AEs will be summarized for all TEAEs, treatment-related TEAEs, TESAEs, treatment-related TESAEs, and AEs resulting in study drug withdrawal or study discontinuation will be tabulated by SOC in alphabetical order and PT in descending order of frequency. Summaries will include count and percent of subjects as well as number of events.

Descriptive statistics summaries of subject incidence of TEAEs by SOC, PT, and relationship to study drug will be provided. Subjects will be counted once under the closest relationship reported within each SOC and PT. Events will be counted the number of times they occur within each SOC and PT.

Descriptive statistics summaries of subject incidence of TEAEs by SOC, PT, and severity will be provided. Subjects will be counted once under the highest severity reported within each SOC and PT. Events will be counted the number of times they occur within each SOC and PT.

All AEs will be listed by subject. Separate by-subject listings of SAEs and of AEs resulting in study drug withdrawal or study discontinuation will be provided.

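### AEs with missing causality or severity are left out of the treatment-related and by-severity tables, which within an arm can only lower, or leave unchanged, the related-TEAE count

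*Protocol*

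**What the plan says.** Protocol 12.8 covers AEs recorded without a severity grade, without a causality assessment, or without both. These "will be included in the all adverse events analyses, except by severity grade and treatment-related". They stay in the overall AE tables and leave the two breakdowns.

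The SAP does not replace this rule:

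- SAP 8.2: "Missing values will not be imputed, except in the case of determining treatment-emergent status for AEs". The remaining exceptions are concomitant status and incomplete dates. Severity and relationship are not among them.
- SAP 9.5.1, on severity, relationship and seriousness: "All AE data summaries will report these as recorded on the eCRF".
- SAP 9.5.1, relationship table: "Subjects will be counted once under the closest relationship reported within each SOC and PT". Severity table: "Subjects will be counted once under the highest severity reported within each SOC and PT". Neither rule says what happens when nothing was reported, and no row for missing values is described.
- SAP 9.5.1, listings: "All AEs will be listed by subject".
- SAP 10 reports no major departure from the protocol's analyses, so the rule in Protocol 12.8 stands.

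The primary endpoint (Protocol 6.1) is "The incidence and frequency of adverse events over time through end of study using escalating multiple doses in NHVs and in CF patients". It does not depend on relationship or severity.

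**The concern.** A subject whose only potentially drug-related event has no causality assessment remains in the denominator, because the Safety Analysis Set (SAP 6.2) contains everyone dosed, but leaves the numerator of the treatment-related table. In that table an unknown relationship has the same effect as a negative one. The event is not assigned to the Not Related category; it is simply absent.

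Treatment-related TEAEs and treatment-related serious TEAEs are named summaries in Protocol 12.3 and SAP 9.5.1, and readers of a first-in-human study look at them closely. Several cohorts have only four active subjects, so one omitted subject can visibly change the related-TEAE incidence. Without a missing row, the breakdowns may also fail to add up to the all-TEAE table, with nothing to tell the reader why.

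**Working it through.** **Inputs**

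- Active subjects (Protocol 7.1, Table 4): 4 in each of Cohorts 1–4, 2b and 3b; 8 in Cohort 5; 9 in Cohort 4b; 18 in Cohort 6.
- Placebo is pooled by population (Protocol 12.3). For CF this gives 2 + 2 + 3 + 6 = 13.
- Per-subject probability *p*: Protocol 12.1 uses 20% and 30% for any TEAE. I borrow 30% as an assumed probability of a *related* TEAE.
- Share *m* of subjects with a related TEAE who lose that status through missing causality: not given in the documents. I assume 0% to 20%.

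**1. Direction within an arm.** Let *R* of *n* subjects have a related TEAE, and let *L* be those whose related TEAEs all lack a causality assessment. The table shows (*R* − *L*)/*n*. Since *L* ≥ 0, this is never above *R*/*n*. If the omitted event was truly unrelated, *L* is unchanged and nothing is understated.

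**2. Size for one omitted subject.** The drop is 1/*n*:

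- *n* = 4: 1/4 = 25 points
- *n* = 8: 1/8 = 12.5 points
- *n* = 9: 1/9 = 11.1 points
- *n* = 18: 1/18 = 5.6 points

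These are upper limits. Incidence counts subjects, so there is no drop if the subject has another TEAE recorded as related.

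**3. Chance that the related table shows anyone.** The plan's own figure comes first: Protocol Table 5 gives 0.76 for *n* = 4 and *p* = 0.3, and 1 − (1 − 0.3)^4 = 0.7599, so it reproduces. The other 13 entries do too. Replacing *p* by *p*(1 − *m*), with *p* = 0.30:

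| Active *n* | *m* = 0 | 5% | 10% | 20% |
|---|---|---|---|---|
| 4 | 0.760 | 0.739 | 0.716 | 0.666 |
| 9 | 0.960 | 0.951 | 0.941 | 0.915 |
| 18 | 0.998 | 0.998 | 0.997 | 0.993 |

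The loss is modest at *n* = 4 even for a high *m*, and negligible in Cohort 6.

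**4. Contrast with placebo.** The rule applies to both arms. Take a hypothetical 6/18 active in Cohort 6 against 4/13 pooled CF placebo:

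- nothing omitted: 33.3% − 30.8% = +2.6 points (from unrounded rates)
- two active subjects omitted: 4/18 − 4/13 = 22.2% − 30.8% = −8.5 points (unrounded)
- two placebo subjects omitted: 6/18 − 2/13 = 33.3% − 15.4% = +17.9 points

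In expectation, with assumed true rates of 30% and 20% (+10 points):

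- 10% missing in both arms: 27 − 18 = +9
- 20% missing in active only: 24 − 20 = +4
- 20% missing in placebo only: 30 − 16 = +14

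The difference can therefore shrink or grow.

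**5. The SAP's other conventions.**

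- Start date wholly missing, and unclear whether the event ended before dosing: SAP 8.2 sets the start to the first dose. The doubt is resolved toward treatment-emergent.
- Several relationships or grades for one subject: SAP 9.5.1 takes the closest relationship and the highest severity.
- No relationship or grade at all: the event is omitted.

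Only the last resolves doubt away from caution. One AE could be made treatment-emergent by the date rule and then disappear from the related table.

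**The case against.** The strongest reply is that the effect is small and disclosed. Protocol 11.5.1 and 11.5.2 require severity and causality for each AE. Causality must be assessed before an SAE form is sent and given in the initial report (11.5.2, 11.7.1), so the table of related serious events should hardly be touched. Data quality control (12.7) and data queries (14.1) should close most remaining gaps. No formal hypothesis test is planned (SAP 2.2), and the stopping criteria in Protocol 7.4 act on individual cases rather than on these tables. All of this stands, and it is why the point is minor.

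Three stronger readings are tempting, and the documents do not support them.

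- *The rule can only understate drug-related harm.* This holds for the related count within one arm. It fails for the comparison with placebo (step 4). It also does not carry over to severity: a missing grade says nothing about whether the drug caused the event.
- *The primary endpoint is biased.* It counts all AEs, and Protocol 12.8 keeps these events in the all-AE analyses. The listings keep them too.
- *The SAP refuses all imputation.* The words "Missing values will not be imputed" are followed by exceptions, one of which settles treatment-emergent status cautiously. The gap concerns severity and relationship only.

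It can also be said that worst-case counting brings its own distortion. For severity this is persuasive: treating a missing grade as severe would create a severe AE out of a data gap and could move the severe rate by 25 points when *n* = 4. For relationship it has less force, since the treatment-related table is a single yes-or-no summary and the SAP already takes the closest relationship among several. Counting a truly unrelated event as related would overstate the rate, so the number of events counted this way should be shown.

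**Conclusion.** The point holds in a narrow form. The protocol's rule, which the SAP leaves in place, can only lower or leave unchanged the related-TEAE count within an arm, and it is out of line with the SAP's own cautious conventions. The most that one omitted subject can do is 25 points with 4 active subjects, 11 with 9 and 5.6 with 18, provided that the subject has no other related TEAE. The overall effect cannot be estimated, because the documents give no rate of missing assessments; the 0% to 20% range and the 30% related-TEAE probability used above are assumptions. Mandatory assessment suggests few such records. The primary endpoint and the listings are unaffected, and the direction of any effect on the active–placebo contrast is not fixed. This is a cheap improvement, not a threat to the study's conclusions.

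**What to change.** Change Protocol 12.8 and SAP 8.2 and 9.5.1 together:

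- **Missing relationship:** count the TEAE as treatment-related in the summary tables, with a footnote giving the number of events counted this way. The relationship table has two related categories (possibly and probably), so the SAP should say which one receives these events.
- **Missing severity:** keep the TEAE in the by-severity table in a row of its own for missing grades. A subject goes in that row only if none of their events in that SOC and PT has a grade.
- **Listings:** show both attributes as missing, without substitution.
- **Consistency:** amend the sentence in SAP 9.5.1 that reports these attributes as entered on the eCRF, so that it allows for the relationship rule.

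The cost is a sentence or two in each document and a small change to the table shells. Related-TEAE figures may become slightly less favourable. Settling the rule before unblinding avoids having to choose it once the affected records and their arms are known.

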13. STUDY APPROVAL AND CONDUCT

The following conditions will be met.

13.1. Regulatory Approval

The requirements for the conduct of clinical trials in accordance with local applicable regulations will be met before commencement of this study.

13.2. Ethics Committee (EC)/ Institutional Review Board (IRB) Approval

Prior to initiation of the study, written EC/IRB approval of the Protocol and Informed Consent Forms, based on the principles of ICH cGCP procedures, will be received. A copy of the signed and dated letter of approval will be provided to the clinical site and ArrowheadPharmaceuticals,

Inc. prior to study commencement. Any written information and/or advertisements to be used for volunteer recruitment will be approved by the EC/IRB prior to use. A list of the EC/IRB voting members, their titles or occupations, FWA number (where applicable) and their institutional affiliations will be requested before study initiation.

Protocol modifications that may impact patient safety or the validity of the study will be approved by the IRB, following written agreement from the Sponsor.

13.3. Ethical Considerations

This study will be carried out per the Declaration of Helsinki 1964, as modified by the 64th World Medical Assembly, Fortaleza, Brazil, October 2013, the Notes for Guidance on Good Clinical Practice (cGCP) (2000) (CPMP/ICH/135/95), and the Principles of the ICH cGCP. The protocol will be submitted for approval to the EC/IRB, and written approval obtained before subjects are enrolled. The composition of the EC/IRB will also be provided to the Sponsor. If approval is suspended or terminated by the IRB, the PI will notify the Sponsor immediately

Where applicable, the clinical site and Arrowhead Pharmaceuticals, Inc. agree to abide by the local compensation guidelines for injury resulting from participating in a company-sponsored research project. Compensation will only be provided on the understanding that the provision of compensation does not amount to an admission of legal liability and is subject to the proposed recipient signing a full and complete release of the company from all claims, damages and costs.

13.4. Written Informed Consent

Informed consent will be obtained before the patient can participate in the study. The contents and process of obtaining informed consent will be in accordance with all applicable regulatory requirements. Study participation includes all screening procedures, as well as any wash-out of excluded medications.

It is the responsibility of the PI (or medically qualified designee) to obtain a written informed consent from everyone participating in this study after adequate explanation of the aims, methods, objectives, and potential hazards of the study. The PI (or medically qualified designee) must also explain to the participants that they are completely free to refuse to enter the study or to withdraw from it at any time. Appropriate forms for documenting a written consent will be provided by the PI or by Arrowhead Pharmaceuticals, Inc.

For this study, each eligible participant will be required to provide written informed consent before participation in the study.

All eligible participants will have the study explained by the PI or designee. They will receive a full explanation, in lay terms, of the aims of the study, the discomforts, risks and benefits in taking part as well as of insurance and other procedures for compensation in case of injury. It will be explained that the study is for research purposes only and is not expected to provide any therapeutic benefit to the individual. It will be pointed out that they can withdraw from the study at any time without prejudice. Each participant will acknowledge receipt of this information by giving written informed consent for participation in the study. The volunteer will be given a copy of the signed Informed Consent Form to retain.

13.5. Emergency Contact with Principal Investigator

Suitable arrangements will be made for participants to contact the PI or medically trained designee in the event of an emergency.

13.6. Notification of General Practitioner

It is the responsibility of the PI or designee, to notify, where applicable, with the consent of the participant, the general practitioner of the patient's participation in the trial, by sending a letter stating the nature of the trial, treatments, expected benefits or adverse events and concomitant drugs to be avoided.

13.7. Clinical Laboratory Certification and Reference Ranges

Before the initiation of this study, the PI, or designee, will obtain a copy of the certification form, with certification number and expiration date for all clinical laboratories (excluding central laboratories) used in the study. Reference ranges for each clinical laboratory test used in this study will be obtained from the appropriate laboratory, which will perform the test for the study.

13.8. Protocol Deviations

A protocol deviation is defined as any intentional or unintentional change to, or noncompliance with, the approved protocol procedures or requirements. The PI will conduct the study in compliance with the approved protocol and will not implement any deviation from or changes to the protocol without prior agreement by the Sponsor and review and documented approval from the EC/IRB of an amendment, except where necessary to eliminate an immediate hazard to study patients.

Deviations may result from the action or inaction of the participant, PI, or site staff. Examples of deviations include, but are not limited to:

- Failure to adhere to study exclusion and inclusion criteria
- Failure to comply with dispensing or dosing requirements
- Use of medications, food, drink, herbal remedies, or supplements that are specifically prohibited in the protocol
- Missed or out-of-window visits
- Drug dosing not administered within the time frame specified in the protocol
- Failure to adhere to test requirements, including vital signs, laboratory tests, physical examinations, PK blood draws, medical history, etc. – either tests not done, incorrect tests done, or not done within the time frame specified in the protocol

Protocol deviations impacting patient safety or eligibility will be reported to the Sponsor or CRO within 2 business days of occurrence and to the EC/IRB /competent regulatory authority per local regulatory requirements.

The PI is responsible for ensuring that any known protocol deviations are recorded and reported as agreed.

